### 5.3. Training

The training of applicable clinical site personnel will be the responsibility of the Sponsor. Prior to initiating subject enrollment at a site, appropriate study training will be provided. Investigators selected to participate in the study will be experienced in intracardiac mapping and AF ablation with balloon and/or focal ablation catheters. Investigators will undergo device training in accordance with the physician training charter.

[figure not shown]
To ensure uniform data collection and protocol compliance, the Sponsor will conduct a training session that will include reviewing the protocol, eCRF and data collection process, and the adverse event reporting process. The sponsor will reinforce the training or provide clarification throughout the study, as needed.

[figure not shown]

[figure not shown]

[figure not shown]

[figure not shown]

[figure not shown]

[figure not shown]

[figure not shown]

## **7. Study Medications**

### **7.1. Antiarrhythmic drugs**

During this study, current AF management guidelines and the institution's standard of care practices are to be followed as closely as possible for AAD therapy.

A Class I and/or Class III AAD can be administered for AF and terminated before the end of the 3-month follow-up visit window (i.e., day 104). If a Class I/III AAD is prescribed/administered after day 104 post procedure or oral amiodarone is prescribed/administered at any time post procedure, it MUST be accompanied by documentation of arrhythmia. If a Class I and/or Class III AAD is continued or started past Day 104, the subject will be considered a primary effectiveness failure. If oral Amiodarone is prescribed and/or taken at any time post index ablation procedure, the subject will be considered a primary effectiveness failure.

Table 7.1A illustrates the corresponding status of primary effectiveness endpoints based on AAD therapy administered in the blanking and post-blanking periods.

[figure not shown]

**Table 7.1A: AAD Usage and Impact on Primary Effectiveness Classification**

	≤ 104 days post procedure	> 104 days post procedure
Class I and/or Class III AAD	Can be initiated, continued from prior to study enrollment, or increased in dose as long as the AAD is stopped on or before day 104 post procedure and subject will not be classified as a primary effectiveness failure.	If initiated for the treatment of AF ; subject will be classified as a primary effectiveness failure .  If initiated for the treatment of AF prior to and continued past Day 104; Subject will be classified as a primary effectiveness failure  Can be initiated, continued from Day 104, or increased if drug is NOT for the treatment of atrial arrhythmia (e.g. premature ventricular contractions, ventricular arrhythmias,) other than CTI dependent AFL and subject will not be classified as a primary effectiveness failure.
Class II and/or Class IV AAD	Can be initiated, continued from prior to study enrollment, or increased in dose and subject will not be classified as a primary effectiveness failure.	Can be initiated, continued from prior to study enrollment, or increased in dose and subject will not be classified as a primary effectiveness failure.
Amiodarone (oral)	If prescribed and/or taken post index ablation procedure subject will be considered a primary effectiveness failure .	

## 7.2. Study specific anticoagulation requirements

- PRIOR to an ablation procedure that uses the HELIOSTAR™ catheter
  - Uninterrupted anticoagulation therapy **MUST** be in place at least 1 month prior to ablation procedure for warfarin/coumadin and 3 weeks for novel oral anticoagulation (NOAC) therapy.
    - If a subject is receiving warfarin/coumadin therapy, they **MUST** be maintained on warfarin/coumadin for at least 4 weeks prior to treatment with a weekly international normalized ratio (INR) ≥ 2 (to be confirmed maximum 48 hours pre-procedure). Any INR < 2 within 3 weeks prior to ablation will lead to exclusion of the subject or postponement of the study procedure until the INR is ≥ 2 for at least 3 weeks prior to treatment.
      - NOTE: If a subject is receiving warfarin/coumadin therapy and the anticoagulation therapy is changed to heparin or an equivalent agent due to documented elevated INR, this will be considered continuous anticoagulation therapy and the subject may proceed with the study procedure even if the INR falls below 2 while the subject is still receiving alternate therapy.
    - If a subject is receiving NOAC therapy, they **MUST** be maintained on recommended doses of anticoagulation for at least 3 weeks prior to the procedure day.

- FOLLOWING an ablation procedure that uses the HELIOSTAR™ catheter
  - Anticoagulation therapy is strongly recommended for at least 2 months following ablation.
  - Decisions regarding continuation of systemic anticoagulation beyond 2 months post ablation should be based on the subject's stroke risk profile.
  - Systemic anticoagulation **will be** continued beyond two months post-procedure in subjects with a CHA2DS2-VASc score of  $\geq 2$  (unless deemed contraindicated based on clinical considerations).

## 8. Study Schedule, Procedures, and Assessments

### 8.1. Screening and Informed Consent

The Patient ICFs used must have approval from Biosense Webster and the study site's IRB/EC prior to patient enrollment in the study. An approved Patient ICF may be translated as appropriate. A copy of a blank approved Patient ICF must be maintained by each investigator in a designated study administrative file.

Patients presenting to the institution with symptomatic PAF and who are considered for an ablation procedure should be pre-screened by the investigator or designated member of the research team for study eligibility per the protocol inclusion and exclusion criteria that can be evaluated as part of the patients' standard of care. Sites should pre-screen all patients who require a documented ablation procedure for symptomatic PAF without regard to sex or race. A pre-screening log will be used to document all patients who were reviewed for potential inclusion into the study.

The study investigator or designee will obtain written informed consent from the patient, or patient's legal representative if applicable, prior to the patient's participation in the study. The patient should NOT undergo any study specific tests or examinations that fall outside the standard of care without first signing the Patient ICF for this clinical investigation. Patients should be made aware that by signing the ICF, they are granting approval for study personnel to review their medical records and to collect/analyze personal medical information. Patients should also be informed that study personnel will maintain confidentiality of the medical records at all times. The background of the proposed study and the potential benefits and risks of the study should be explained to the patient before the ICF is signed.

If a patient is unable to read or write, informed consent shall be obtained through the aid of an independent witness who will be present throughout the process. The written Patient ICF and any other information shall be read aloud and explained to the prospective patient and, whenever possible, the patient shall sign and date the ICF. The independent witness

must also sign and date the ICF attesting that the information was accurately explained and that consent was freely given.

The investigator and/or designee must also clearly document the process of obtaining informed consent in the patient's source documents. The voluntary process of informed consent confirms the patient's willingness to participate in the study. It's the investigator's responsibility to ensure that the informed consent process is performed in accordance with GCP, 21 CFR Part 50, ISO14155, and with applicable local and federal regulations. If new information becomes available that can significantly affect a study subject's future health and/or medical care, this information shall be provided to the subject(s) affected. If relevant, all affected subjects shall be asked to confirm their continuing informed consent in writing by dating and signing an amended Patient ICF.

[figure not shown]
## 8.2. Pre-Procedure/Baseline Assessments, Evaluations and Procedures

[figure not shown]
Assessments and data that **MUST** be collected prior to the ablation procedure are described below. Assessments/data should be completed within 90 days prior to the study ablation procedure, unless otherwise specified.

[figure not shown]
- **Demographics:** Including but not limited to age, race (where allowed), ethnicity (where allowed), and gender.
- **Medical History:** Including arrhythmia, heart disease, thromboembolic events, lung/respiratory problems, etc.
- **AF History:** Including the first evidence of AF, number of episodes, symptoms, etc.
- **NYHA:** NYHA Classification will be used to assess the extent of heart failure for subjects with congestive heart failure.
- **CHA2DS2 VASc Score:** Will be used to assess the risk of stroke.
- **Medication History:** Medication history (cardiac medication, AAD medication, anticoagulation regimen and any other clinically significant medication history) shall be gathered by interview or from medical records following enrolment but prior to the ablation procedure and should be recorded in the eCRF.
- **Anticoagulation Therapy:** Anticoagulation therapy information shall be gathered by interview or collected from medical records following enrolment but prior to the ablation procedure.
- **Height and weight** will be measured.
- **Physical Exam (including standardized neurological assessment and cardiovascular/ pulmonary examination):** Exam should be performed by a physician prior to the ablation procedure. The following items will be evaluated as part of the standardized neurological assessment: vision, hearing, speech, level of consciousness, orientation and ability to move all extremities.
- **Electrocardiogram:** Data from 12-lead ECG recordings will be collected if available.
- **Transthoracic Echocardiogram (TTE):** TTE will be used to determine the atrial size and left ventricle ejection fraction (LVEF). Equivalent exams may be substituted if needed and clinically acceptable.
- **Cardiac Multi Slice Computed Tomography (CT) or Magnetic Resonance Angiogram (MRA) image:** CT/MRA **MUST** be of sufficient quality to evaluate the number, size and anatomy of the pulmonary veins and the left atrial anatomy. It is mandatory to conduct the CT/MRA assessment within 6 months prior to the study ablation procedure. All CT/MRA images collected for the study should be sent to the study core lab. For subjects in the CT/MRA subset and those with symptoms of PV stenosis, a core lab will determine the following measurements:

- Major axis (mm)
  - Minor axis (mm)
  - Average diameter (mm)
- **Left Atrial Thrombus Detection:** Imaging for detection of left atrial thrombus or other structural contraindications to an ablation procedure is mandatory the day before or the day of the ablation procedure. Presence of a thrombus will require postponement of the ablation procedure or exclusion of the subject from further study involvement. The imaging methods to be used for atrial thrombus detection are TEE or ICE.
- **Pregnancy Test: MUST** be done for all women of childbearing age and potential within 72 hours prior to the ablation procedure.
- **Quality of Life (AFEQT™):** AFEQT™ **MUST** be collected prior to procedure.
- **Adverse Events:** AEs **MUST** be collected from the time the subject signs the informed consent onwards.
- **Neurological Assessment (NAE Subjects only):** The following assessment are required to be performed within 72 hours pre-procedure for subjects included in the NAE subset, including:
  - Cerebral MRI (see appendix A for methodology)
  - Neurological Exam
  - National Institutes of Health Stroke Scale (NIHSS)
  - Modified Rankin Scale (mRS)
  - Mini-Mental State Examination (MMSE)

NIHSS and mRS assessments will be performed by a site staff certified in the administration of the assessments. The MMSE will be performed by site staff with documented training in the administration of such tools. A certified neurologist, blinded to the cerebral MRI data, will perform neurologic exams. Cerebral MRIs will be analyzed by a central core lab to determine the frequency, size, and anatomical location of cerebral micro-emboli, if any.

### 8.5. Repeat Procedures

Repeat procedures may be performed at the discretion of the investigator. Repeat procedures during the blanking period (90 days post index procedure) must be conducted with the investigational device, with or without focal touch-up, if the arrhythmia is due to PV triggers. Repeat procedures performed after the blanking period may be managed per investigator discretion using a commercially available ablation catheter and generator. The follow-up schedule will remain based on the initial ablation procedure. All pre-discharge and 7-day post-ablation assessments as summarized in Table 8.8A are to be collected for repeat procedures.

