### Endpoint:

#### Primary Endpoints:

- **Safety**

Incidence of early onset Primary Adverse Events (PAEs) (within 7 days of an ablation procedure which uses the HELIOSTAR™ catheter). PAEs include the following adverse events (AEs) and are defined in section 9.2.3 of the protocol:

- Device or procedure related death\*
- Atrio-Esophageal Fistula\*
- Myocardial Infarction
- Cardiac Tamponade/Perforation\*
- Thromboembolism
- Stroke/ Cerebrovascular Accident (CVA)
- Transient Ischemic Attack (TIA)
- Phrenic Nerve Paralysis (permanent)
- Pulmonary Vein Stenosis\*
- Pericarditis
- Pulmonary Edema
- Major Vascular Access Complication/Bleeding
- Hospitalization (initial or prolonged)\*\*

\* Events are considered and analyzed as primary AEs **even if they occur greater than one week (7 days) post-procedure.**

\*\* Excludes hospitalization solely due to arrhythmia recurrence or non-medically urgent cardioversion.

- **Effectiveness**

Freedom from documented asymptomatic and symptomatic Atrial Fibrillation, Atrial Tachycardia, or Atrial Flutter of unknown origin+ episodes based on electrocardiographic data (≥30 seconds on arrhythmia

monitoring device) through the effectiveness evaluation period (91-365 days post index procedure). Additionally, if a subject meets any one of the following criteria, then the subject will be considered an effectiveness failure:

- Failure to achieve acute procedural success. Acute procedural success is defined as confirmation of entrance block in clinically relevant PVs (all PVs except those that are silent and/or cannot be cannulated) after adenosine and/or isoproterenol challenge (with or without the use of a focal catheter).
- Greater than 2 repeat ablations for AF/AT/AFL (of unknown origin\*) in the blanking period ( $\leq 90$  days post index procedure) or a repeat ablation or surgical treatment for AF/AT/AFL (of unknown origin\*) during the effectiveness evaluation period.
- Direct current (DC) cardioversion for AF/AT/AFL (of unknown origin\*) during the effectiveness evaluation period.
- Continuous AF/AT/AFL (except CTI dependent) on a standard 12-lead ECG during the effectiveness evaluation period.
- A Class I and/or Class III AAD is prescribed/taken for atrial arrhythmia other than CTI dependent AFL at any time beyond the 3-month follow-up visit window (i.e., at any time beyond day 105 to 365 post index procedure).
- Oral Amiodarone is prescribed post index ablation procedure.

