- **Electrocardiogram (12-Lead ECG):** Data from 12-lead ECG recordings will be collected at the 3M and 12M follow-up visit. ECG data will be collected at baseline, pre-discharge, 1M follow-up visit, and unscheduled visits if completed as standard of care and at 6M if a clinical visit occurs and ECG is completed as standard of care. If an ECG is unable to be obtained (e.g. due to telemedicine visit), subjects will be instructed to transmit 1 TTM transmission (60 seconds) in lieu of an ECG recording at the time of the follow-up visit. Any 12-lead ECG tracings obtained beyond 3 months (90 days) showing an arrhythmia will be reviewed and adjudicated by an independent cardiologist.
- **Transtelephonic Monitoring (TTM):** Subjects will be provided with a TTM device no later than at the 1M follow-up visit (TTM device may be provided at discharge if collected as standard of care) and required to record and transmit a minimum of 1 transmission (60 seconds) every week through the end of month 5 of follow-up. Starting at month 6 of follow-up, subjects will be required to record and transmit a minimum of 1 transmission (60 seconds) every month until the effectiveness evaluation period is completed (12 months post index procedure). Subjects will also be instructed to transmit any symptom-triggered episode that occurs from the time they receive the TTM device through the 12M follow-up visit. A core lab will be used to evaluate and assess the TTM tracings.
- **24 Hour Holter:** Holter monitor will be used at the 12M follow-up visit to monitor the subjects' heart rhythm for 24 hours continuously. A core lab will be utilized to evaluate and assess the 24-hour Holter recordings.
- **Cardiac Multi Slice CT/MRA Image:** CT/MRA will be completed at the 3M follow-up visit for subjects in the CT/MRA subset. In addition, any subjects who have symptoms suggestive of PV stenosis should undergo CT/MRA imaging. Post procedure CT/MRA should be performed with contrast, unless there is a contraindication, and must be of sufficient quality to evaluate the number, size and anatomy of the pulmonary veins. All CT/MRA images collected for the study should be sent to the study core lab.
- **Adverse Events:** AEs must be collected from the time the subject signs the informed consent onwards.

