**Table 8.8A: Summary of Subject Assessments**

Assessments	Pre- Procedure	Pre- Discharge Post procedure - Discharge	D7  D7- 14	M1 D23- 37	M3 D76- 104	M6  D150- 210	M12 D315- 405	UNS
Patient Informed Consent/ Demographics	● 							
Height and Weight	● 							
Physical exam	● 	●		●	●	● 	●	●
Medical/AF history	● 							
Cardiac Medication Regimen 	● 	●	●	●	●	●	●	●
Anti-coagulation Regimen 	● 	●		●	●	●	●	●
CHA 2 DS 2 -Vasc Score	● 							
NYHA functional Class Scale	● 							
Pregnancy Test	● 							
QoL (AFEQT™ questionnaire) 	● 				●	● 	●	
TTE	● 	● 						
LA thrombus detection (TEE/ICE)	● 							
ECG	● 	● 		● 	●	● 	●	● 
TTM 				●	●	●	●	●
24-hour Holter 							●	
Cardiac CT/MRA	● 				● 			● 15a
Adverse events 	●	●	●	●	●	●	●	●
AFL/AT/AF recurrence 				●	●	●	●	●
Repeat Ablation				●	●	●	●	●
Cerebral MRI (NAE subjects only)	● 	● 		● 	● 	● 	● 	● 
Neurological Exam (NAE subjects only)	● 	● 		● 	● 	● 	● 	● 
NIH Stroke Scale (NAE subjects only)	● 	● 		● 	● 	● 	● 	● 
mRSE (NAE subjects only)	● 			●	● 	● 	● 	● 
MMSE (NAE subjects only)	● 			●	● 	● 	● 	● 

1. May be telephone call, virtual visit, or clinic visit.
2. Completed/Collected within 90 days prior to ablation procedure.
3. Required only for clinical visit
4. May be completed via telephone call or virtual visit when a clinic visit is not possible.
5. Completed/Collected in subjects with congestive heart failure.
6. In all women of childbearing age and potential. To be completed within 72-hours prior to ablation procedure.
7. To be completed within 48 hours post-index procedure.
8. To be completed the day before or the day of the study ablation procedure.

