### 9.2.3. Primary Adverse Event

A Primary AE is an event listed in Table 9.2.3A which occurs within the first week (7 days) of an ablation procedure which used one or more of the investigational device(s) unless otherwise indicated.

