Pulmonary Vein Stenosis*	Severe PV stenosis ( $\geq 70\%$ reduction in the diameter of the PV) will be considered a primary adverse event and major complication of AF ablation.
Phrenic Nerve Paralysis	Absent phrenic nerve function as assessed by a sniff test. A phrenic nerve paralysis is considered to be permanent when it is documented to be present 12 months or longer following ablation.
Major Vascular Access Complication / Bleeding	Major Vascular Access Complication: Defined as a hematoma, an AV fistula or a pseudoaneurysm which requires intervention such as surgical repair or transfusion, prolongs the hospital stay, or requires hospital admission. Major Bleeding: A major complication of AF ablation if it requires and/or treated with transfusion or results in a 20% or greater fall in HCT.
Pericarditis	Major: results in effusion which leads to hemodynamic compromise or requires pericardiocentesis, prolongs hospitalization by more than 48 h, requires hospitalization, or persists for more than 30 days following the ablation procedure.
Pulmonary Edema (Respiratory Insufficiency)	Respiratory insufficiency resulting in pulmonary complications necessitating intubation or other significant intervention (including diuretics administered specifically for treating pulmonary edema or ICU hospitalization requiring oxygen administration but not intubation). Pneumonia (infiltrate, fever and leukocytosis) and Acute Respiratory Distress Syndrome are excluded from this definition.

Primary Adverse Event	Description / Criteria

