Stroke/ Cerebrovascular Accident (CVA)	
Diagnosis:
 
 
• Rapid onset of a focal or global neurological deficit with at least one of the following: change in level of consciousness, hemiplegia, hemiparesis, numbness or sensory loss affecting one side of the body, dysphasia or aphasia, hemianopia, amaurosis fugax, or other neurological signs or symptoms consistent with stroke.
 
• Duration of a focal or global neurological deficit <math>\geq 24</math> h; or <math>< 24</math> h, if therapeutic intervention(s) were performed (e.g., thrombolytic therapy or intracranial angioplasty); OR available neuroimaging documents a new hemorrhage or infarct; or the neurological deficit results in death.
 
• No other readily identifiable non-stroke cause for the clinical presentation (e.g., brain tumor, trauma, infection, hypoglycemia, peripheral lesion, pharmacological influences).†
 
• Confirmation of the diagnosis by at least one of the following: Neurology or neurosurgical specialist; Neuroimaging procedure (MRI or CT scan or cerebral angiography); Lumbar puncture (i.e., spinal fluid analysis diagnostic of intracranial hemorrhage).
 
 
Definition: Stroke: (diagnosis as above, preferably with positive neuroimaging study)
 
 
• Minor—Modified Rankin score <math>< 2</math> at 30 and 90 days††
 
• Major—Modified Rankin score <math>\geq 2</math> at 30 and 90 days
 

Hospitalization (initial or prolonged)	Device or procedure related serious adverse event that prolongs or requires in patient hospitalization for more than 48 hours. Excludes hospitalization (initial & prolonged) solely due to arrhythmia (AF/AFL/AT) recurrence or due to nonurgent cardioversion (pharmacological or electrical).

\* Occurrence greater than one week (7 days) post-procedure shall be deemed Primary AE.

\*\* Hemodynamic compromise or instability is defined as Systolic blood pressure  $< 80$  mmHg

† Non-focal global encephalopathy will not be reported as a stroke without unequivocal evidence based upon neuroimaging studies.

†† mRS assessments should be made by qualified individuals according to a certification process. If there is discordance between the 30 and 90 day mRS, a final determination of major versus minor stroke will be adjudicated by an independent physician/committee.

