1 STUDY DESIGN

This clinical investigation is a prospective, multicenter, single arm clinical evaluation utilizing the Biosense Webster HELIOSTAR™ catheter, in conjunction with the LassoStar™ catheter and Multi-Channel RF Generator, for the treatment of drug refractory symptomatic paroxysmal atrial fibrillation (PAF) with pre-specified performance goals for safety and effectiveness.

An adaptive Bayesian design will be used to determine the sample size. Up to a maximum of 400 evaluable subjects with symptomatic PAF may be enrolled in the main study phase.

To minimize the learning curve effect on the evaluation of safety and effectiveness of the HELIOSTAR™ catheter, a maximum of 240 roll-in subjects will be enrolled in the study. One (1) to three (3) roll-in subjects will be prospectively assigned to each ablating physician per the physician training charter. These subjects will not be counted towards the enrollment cap of 400 evaluable subjects. All subjects will be evaluated at 7 days, 1, 3, 6 and 12 months following the index procedure. Data for roll-in subjects will be analyzed separately from the main phase.

A focused neurological evaluation will be integrated within the Main Study. Forty (40) subjects enrolled in the main study will be included in the Neurological Assessment Evaluable (NAE) subset. NAE subjects will be assessed for incidence of post-ablation symptomatic and asymptomatic cerebral emboli.

Forty (40) subjects enrolled in the main study will be included in the CT/MRA subset. Subjects in the CT/MRA subset will undergo the CT/MRA exams at baseline and 3 months post ablation procedures for the assessment of PV stenosis. A subject may be permitted to participate in both the NAE and CT/MRA assessments.

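### A repeat HELIOSTAR ablation counts for primary safety, but the one scheduled PV-stenosis scan is timed from the index procedure and may not reflect the last ablation

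*Protocol*

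**What the plan says.** **What is counted.** The Protocol Summary defines the primary safety endpoint by events "within 7 days of an ablation procedure which uses the HELIOSTAR™ catheter". Section 9.2.3 likewise refers to an "ablation procedure which used one or more of the investigational device(s) unless otherwise indicated". Repeats with the device are therefore included. PV stenosis is starred in Table 9.2.3A, and the footnote reads "Occurrence greater than one week (7 days) post-procedure shall be deemed Primary AE". The stenosis that counts is a diameter reduction of 70% or more, which takes imaging to establish.

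**Which repeats occur.** Section 8.5 requires the study device for repeats within 90 days of the index procedure when PV triggers are the cause. The effectiveness definition tolerates two repeats in that period.

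**How follow-up is anchored.** Section 8.5: "The follow-up schedule will remain based on the initial ablation procedure". Sections 8.6 and 8.7 say the same in other words. After a repeat, section 8.5 asks for the pre-discharge and 7-day assessments again.

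**When the veins are imaged.** Section 8.6: "CT/MRA will be completed at the 3M follow-up visit for subjects in the CT/MRA subset". Any subject with symptoms suggesting PV stenosis should also be scanned. SAP section 1 says that the 40 subset subjects "will undergo the CT/MRA exams at baseline and 3 months post ablation procedures for the assessment of PV stenosis".

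**Echocardiography.** Table 8.8A lists the TTE under pre-discharge, with footnote 7: "To be completed within 48 hours post-index procedure". Section 8.6 also ties it to the index procedure.

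**The concern.** The endpoint follows the device: each HELIOSTAR procedure opens a new period in which a primary adverse event can arise. The scheduled search for late events follows the index date. The two agree for a subject treated once. For a subset member treated again in the blanking period, the single scheduled scan may be taken before the last ablation, or so soon after it that it says little about that ablation.

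What is at stake is how the subset's stenosis result can be read. The subset provides the trial's only scheduled post-ablation imaging of the veins. A scan taken before a repeat cannot show stenosis that the repeat causes. In a group of 40, one subject is 1/40 = 2.5 percentage points.

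A smaller issue is contact. After an index procedure the plan has a visit at day 23-37; nothing comparable is tied to a repeat.

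**Working it through.** **Inputs.** Visit windows from Protocol section 8.6; blanking period of 90 days from section 8.5; subset of 40 from SAP section 1. The repeat rate is not given in the public text, so 3-10% is assumed.

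**1. Reproduce the plan's windows.** With 30-day months: 30 ± 7 = 23-37; 90 ± 14 = 76-104; 180 ± 30 = 150-210; 360 ± 45 = 315-405. All four match.

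**2. Scan time relative to a repeat on day r.** The interval from repeat to scan runs from 76 − r to 104 − r. A negative value means that the scan came first.

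| Repeat on day | Earliest scan | Latest scan |
|---|---|---|
| 30 | 46 days after | 74 days after |
| 60 | 16 days after | 44 days after |
| 76 | same day | 28 days after |
| 90 | 14 days before | 14 days after |

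The scan can precede the repeat when the repeat falls on days 77-90 and the scan was done earlier in its window.

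**3. How many subjects.** 3% × 40 = 1.2 and 10% × 40 = 4, so about 1-4 subset members with any blanking-period repeat. For scan before repeat, assume further that repeats are spread evenly over the 90 days and that every scan is done on day 76, the least favourable case. Days 77-90 are 14 days: 14/90 × 1.2 = 0.2 and 14/90 × 4 = 0.6 subjects.

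**4. Contact after a repeat.** Take the 3-month visit on day 76, a repeat on day 77, the 7-day call on day 84 and the 6-month contact on day 210: 210 − 84 = 126 days. With the 6-month contact on day 180: 180 − 84 = 96 days. For comparison, a subject with no repeat may go from day 76 to day 210: 134 days.

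**5. Echocardiography after a repeat.** Section 8.5 asks for every pre-discharge assessment after a repeat, and the TTE is one of them in Table 8.8A. Section 8.6 and footnote 7 confine it to the index procedure. This touches the endpoint because Table 9.2.3A counts an effusion of 1 cm or more on echocardiography under tamponade/perforation. That definition runs for 30 days from the index procedure, so it raises the same question of anchor for repeats.

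**The case against.** Anchoring on the index date is deliberate: the Protocol states it three times, and it suits the effectiveness endpoint. The 7-day safety window is also covered after a repeat, because the pre-discharge and 7-day assessments are redone. Beyond that, unscheduled visits, adverse-event recording to the end of participation and symptom-driven CT/MRA remain available. All of this stands, and it confines the point to late events, chiefly PV stenosis in the subset.

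Four stronger readings are tempting, and the documents do not support them.

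- *Repeats open a four-month lapse in contact.* The 126 days needs every window at its extreme, and it is shorter than the 134 days that any subject may have. What is left is the absence of a contact like the 1-month visit after a repeat.
- *Most blanking-period repeats leave the scan too early.* Only a repeat by day 28 (104 − 76) can have a scan 76 days later, which leaves 62 of the 90 days. But the visible text sets no minimum interval, and a scan some weeks after a repeat still images the re-treated vein. Nor do the roughly 360 subjects outside the subset belong in the count, since they have no scheduled post-ablation scan under either anchor.
- *The stenosis rate is biased low.* Stenosis missed because the scan came first would be an undercount, but no size can be shown. Section 1.5.1 calls stenosis usually asymptomatic for the hot balloon, another device, without stating severity. It does not show that a 70% narrowing after HELIOSTAR would escape symptom-driven imaging.
- *The SAP contradicts the Protocol on scan timing.* The plural at the end of the SAP phrase most naturally matches plural subjects.

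On the TTE, section 8.5 refers to assessments as summarized in Table 8.8A, so footnote 7 can be read as limiting it. That reading is available but not stated, and a site could equally follow the word for all assessments. Finally, the contents list shows a section 3.1.4 on the CT/MRA subset that is not in the public text. A rule for re-treated subjects may sit there.

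**Conclusion.** The point holds in a limited form. In the visible text, primary adverse events follow every HELIOSTAR procedure, while the single scheduled subset scan follows the index procedure only. For a subset member with a blanking-period repeat, that scan may precede the last ablation (repeat on days 77-90) or follow it closely (at most 14 days after a day-90 repeat). Symptom-driven imaging recovers some such cases but not those without symptoms.

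The size is about 1-4 of 40 subjects with any such repeat, and under one expected with the scan before the repeat. Both figures rest on the assumed 3-10% repeat rate, and the second also on an even spread of repeats. The conclusion depends on section 3.1.4 containing no re-imaging rule, which cannot be checked. The lack of a later adverse-event contact tied to the repeat, and the unclear TTE requirement, are real but secondary.

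**What to change.** 1. **Scan not yet done at the repeat.** In sections 8.5 and 8.6, state that for a CT/MRA-subset member the single follow-up scan is done 76-104 days after the last HELIOSTAR procedure, in place of the index-based scan. For a day-90 repeat this is day 166-194 from index (90 + 76 to 90 + 104), inside the 6-month window.
2. **Scan already done.** Do not add a second one. Flag the subject as not imaged after the last ablation, and state in the SAP that the subset stenosis rate is reported with and without such subjects.
3. **Contact.** Add one adverse-event telephone contact 23-37 days after any HELIOSTAR repeat. Keep the effectiveness schedule on the index date.
4. **Text.** Reconcile section 8.5 with section 8.6 and Table 8.8A footnote 7 on whether the post-procedure TTE applies to repeats. Check the 30-day tamponade wording in Table 9.2.3A at the same time. The documents do not settle which reading is meant; the sponsor must. If section 3.1.4 already has a re-imaging rule, a cross-reference from 8.5 may replace item 1.

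The cost is protocol and SAP wording, one call per repeat, and mixed scan timing for a few subset subjects. Some would attend separately for the scan: a day-40 repeat gives day 116-144 (40 + 76 to 40 + 104), between the 3- and 6-month windows.
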